9.3.3 Start of Double-blind Treatment Period/Randomization

The examinations/observations/assessments listed below will be performed at the start of double-blind treatment period (Day -1; Visit 3). Subjects will be screened in accordance with predefined inclusion and exclusion criteria as described in Section 7.0. Subjects assessed to be eligible will be randomized according to Section 8.2 and enter the double-blind treatment period. See Section 9.1.20 for documenting subjects who prematurely discontinue the study after entry into the placebo lead-in period and prior to randomization.

The examinations/observations/assessments at Visit 3 should be regarded as baseline evaluations.

- Physical examination
- Weight
- Vital signs
- Concomitant medications
- Clinical laboratory tests (fasted)
- Pregnancy test (female subjects of childbearing potential only)
- ECG procedure
- C-SSRS
- PTE/AE assessment
- MADRS
- HAM-D
- CGI-S
- CGI-I (assessed comparing with a CGI score at Visit 2).
- SDS

- DSST
- PDQ-5
- QIDS-J
- Randomization
- Dispense of the study medication (for the double-blind treatment [Inner Carton 1])
- Collection of the study medication dispensed at the last visit/Consultation about subjects' compliance

9.3.4 Double-blind Treatment Period

Visit 4

The examinations/observations/assessments listed below will be performed at 1 week after the start of double-blind treatment period (Day 7 ± 1; Visit 4).

- Vital signs
- Concomitant medications
- C-SSRS
- PTE/AE assessment
- MADRS
- CGI-S
- CGI-I (assessed comparing with a CGI score at Visit 3).
- DSST
- PDQ-5
- QIDS-J
- Dispense of the study medication (for the double-blind treatment [Inner Carton 2])
- Collection of the study medication dispensed at the last visit/Consultation about subjects' compliance

Visit 5

The examinations/observations/assessments listed below will be performed at 2 weeks after the start of double-blind treatment period (Day 14 ± 3; Visit 5).

- Vital signs
- Concomitant medications
- C-SSRS

- PTE/AE assessment
- MADRS
- CGI-S
- CGI-I (assessed comparing with a CGI score at Visit 3).
- QIDS-J
- Dispense of the study medication (for the double-blind treatment [Inner Carton 2])
- Collection of the study medication dispensed at the last visit/Consultation about subjects' compliance

Visit 6

The examinations/observations/assessments listed below will be performed at 4 weeks after the start of double-blind treatment period (Day 28 ± 3; Visit 6).

- Weight
- Vital signs
- Concomitant medications.
- Clinical laboratory tests
- Pregnancy test (female subjects of childbearing potential only)
- Pharmacokinetic sampling
- ECG procedure
- C-SSRS
- PTE/AE assessment
- MADRS
- CGI-S
- CGI-I (assessed comparing with a CGI score at Visit 3).
- QIDS-J
- Dispense of the study medication (for the double-blind treatment [Inner Carton 2])
- Collection of the study medication dispensed at the last visit/Consultation about subjects' compliance

Visit 7

The examinations/observations/assessments listed below will be performed at 6 weeks after the start of double-blind treatment period (Day 42 ± 3; Visit 7).

- Vital signs
- Concomitant medications
- C-SSRS
- PTE/AE assessment
- MADRS
- CGI-S
- CGI-I (assessed comparing with a CGI score at Visit 3).
- QIDS-J
- Dispense of the study medication (for the double-blind treatment [Inner Carton 2])
- Collection of the study medication dispensed at the last visit/Consultation about subjects' compliance

9.3.5 End of Double-blind Treatment Period or Early Termination

The examinations/observations/assessments listed below will be performed at 8 weeks after the start of double-blind treatment period (Day 56 ± 3; Visit 8) as evaluation at the end of double-blind treatment period. Subjects who prematurely discontinue the study during the placebo lead-in period or double-blind treatment period will be requested to visit the study site for early termination examinations/observations/assessments within 7 days after the day of study discontinuation wherever possible.

- Physical examination
- Weight
- Vital signs
- Concomitant medications
- Clinical laboratory tests (fasted)
- Pregnancy test (female subjects of childbearing potential only)
- Pharmacokinetic sampling (not performed at early termination)
- ECG procedure
- C-SSRS
- PTE/AE assessment
- MADRS
- HAM-D
- CGI-S

- CGI-I*
- SDS
- DSST
- PDQ-5
- QIDS-J
- Collection of the study medication dispensed at the last visit/Consultation about subjects' compliance

* The CGI-I score will be assessed comparing with that at Visit 3. However, at early termination prior to Visit 3, the CGI-I score will be assessed by comparing with that at Visit 2.

For all randomized subjects, the investigator must complete the End of Study eCRF page.

After evaluation at the end of double-blind treatment period or early termination, standard therapy may be performed as needed.

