4.1.1 Clinical Pharmacology

Results of clinical pharmacology studies in Japan and overseas are summarized below.

Lu AA21004 was slowly absorbed after oral administration, and the Tmax was approximately 7 to 11 hours. The absolute bioavailability of Lu AA21004 was approximately 75%. The

pharmacokinetics of Lu AA21004 was linear within the dose range between 2.5 and 60 mg. The plasma concentration of Lu AA21004 reached steady state after approximately 2-week multiple doses, and the accumulation index was 5 to 6 based on AUC following multiple doses of 5 to 20 mg/day. There was no food effect on the pharmacokinetics of Lu AA21004.

Lu AA21004 was extensively metabolized in the liver, primarily through oxidation or glucuronic acid conjugation, and CYP2D6 was shown to be the primary enzyme in metabolism of Lu AA21004 to the major metabolite Lu AA34443. Lu AA34443 was pharmacologically inactive, and the active metabolite Lu AA39835 did not cross the blood-brain barrier, although Lu AA39835 was slightly detected in plasma, suggesting that these metabolites are less likely to contribute to the pharmacological effect of Lu AA21004. In addition, Lu AA21004 and its metabolites did not induce or inhibit CYP isozymes *in vitro*, suggesting that clinical significant drug-drug interactions with Lu AA21004 are less likely to occur.

The T1/2 of Lu AA21004 was approximately 66 hours, and two- thirds of its metabolites were excreted in urine, and one-third were excreted in feces. The excretion of unchanged Lu AA21004 was slightly noted in feces.

After multiple doses of Lu AA21004, 5-HTT occupancy in raphe nuclei was approximately 50% at doses of 5 mg/day, 65% at 10 mg/day, and 80% or more at 20 mg/day.

Based on results of studies in Caucasian and Japanese subjects, there were no statistically significant differences in the pharmacokinetics and 5-HTT occupancy of Lu AA21004 between the races.

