4.1.2 Overseas Phase II/III Clinical Studies

A total of 12 overseas placebo-controlled, double-blind, short-term studies (Studies 11492A, 11984A, 303, 304, 305, 13267A, 315, 316, 317, CCT-002, 12541A and 14122A) were conducted to evaluate the efficacy of Lu AA21004 for the treatment of MDD. Study CCT-002 was a multinational study including Japan.

The changes from baseline in the Montgomery-Åsberg Depression Rating Scale (MADRS) total score were analyzed by mixed model repeated measures (MMRM) in the individual studies; and the results of the 11 of 12 studies mentioned above except for Study 12541A for elderly patients were used for meta-analysis. As for the mean changes from baseline in the MADRS total score at Week 6 or 8, the differences of the Lu AA21004 5, 10 and 20 mg group compared to the placebo group were -2.3 (p = 0.007), -3.6 (p < 0.001) and -4.6 (p < 0.001), respectively, and all of them were statistically significant. In addition, although the mean difference between the 15 mg group and placebo group was -2.6, not statistically significant. MADRS response rate (MADRS response is defined as a \geq 50% decrease from baseline in the MADRS total score) in the subjects treated with Lu AA21004 was 46% to 49%, whereas that in the subjects treated with placebo was 34% (p < 0.01). These results suggested Lu AA21004 at doses of 5 to 20 mg/day was effective.

For comprehensive safety evaluation including the above-mentioned short-term studies and long-term studies (Studies 11492C, 11984B, 301, 13267B and 314), treatment with Lu AA21004 at doses of 5 to 20 mg/day was safe and well tolerated. The most common TEAE in the

Lu AA21004 groups was nausea, and gastrointestinal TEAEs were occurred more frequently in female than male. Most TEAEs were mild or moderate and occurred within the first 2 weeks of treatment. In addition, TEAEs were usually transient, and did not generally lead to discontinuation of the study medication.

Abrupt discontinuation of antidepressants may result in discontinuation symptoms, however, there were no clinically relevant differences in the incidence or nature of discontinuation symptoms between the Lu AA21004 groups and placebo group.

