9.1.17 Pharmacokinetic Sample Collection and Analysis

9.1.17.1 Collection of Blood for Pharmacokinetic Sampling

Blood samples will be collected in concurrence with blood collection for clinical laboratory tests. The exact date and time of the blood collection and dosing times of the last 2 doses prior to the blood collection will be recorded on the eCRF. Refer to the separately created procedure for collection, handling, and shipping of blood samples.

Since drug concentrations of subjects in the placebo group will not be measured, the assignment personnel will send an operation manual to the central laboratory to identify samples of subjects in the placebo group. Drug concentration data will be reported to the sponsor after unblinding of the study.

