13.1.4 Pharmacokinetic Analysis

The population pharmacokinetic analysis of Lu AA21004 and its metabolites Lu AA34443 and Lu AA39835 will be performed using the nonlinear mixed effect model (NONMEM). Pharmacokinetic parameters of individual subjects (e.g., AUC[0-tau], Cavg, Cmax) will be estimated and their correlation with relevant pharmacodynamic parameters (efficacy and tolerability/safety) will be explored. The population pharmacokinetic analysis plan will be prepared separately.

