Appendix A Schedule of Study Procedures

	Screening Period	Placebo Lead-in Period ^(a)	Double-blind Treatment Period						Follow-up Period
			3	4	5	6	7	8/ET ^(c)	
Visit Number	1	2							
Week ^(b)	-4 to -2	-1	0	1	2	4	6	8/ET ^(c)	12 ^(d)
Day ^(b)	-32 to -12	-8	-1	7	14	28	42	56/ET ^(c)	84 ^(d)
Visit Window (Days) ^(b)	-	±3	0	±1	±3	±3	±3	±3/-	±5
Informed consent	X ^(e)								
Inclusion/exclusion criteria	X	X ^(f)	X ^(f)						
Demographics, medical history, medication history	X								
Diagnosis of MDD	X								
Assessments of major depressive episode	X								
Physical examination	X	X	X					X	
Weight, height ^(g)	X	X	X			X		X	
Vital signs	X	X	X	X	X	X	X	X	
Concomitant medications	X	X	X	X	X	X	X	X	
Concurrent medical conditions	X								
Clinical laboratory tests ^(h)	X	X	X			X		X	
Pregnancy test ⁽ⁱ⁾	X	X	X			X		X	(-)
Urine drug screening	X	X							
Pharmacokinetic sampling					X			(X)	
Pharmacogenomic sampling ^(j)		(X)							
ECG	X	X	X			X		X	
C-SSRS	X	X	X	X	X	X	X	X	
PTE/AE assessment ^(k)	X	X	X	X	X	X	X	X	(-)
<Assessments with Rating Scales>									
MADRS	X	X	X	X	X	X	X	X	
HAM-D	X	X	X					X	
CGI-S	X	X	X	X	X	X	X	X	
CGI-I ^(l)			X	X	X	X	X	X	
SDS			X	X				X	
DSST ^(m)			X	X				X	
PDQ-5			X	X				X	
QIDS-J			X	X	X	X	X	X	
<Clinical Supply>									
Randomization			X						
Dispense study medication ⁽ⁿ⁾		X	X	X	X	X	X		
Drug return/accountability/compliance			X	X	X	X	X	X	

ET = early termination

- (a) In the placebo lead-in period, subjects will receive the study medication in a single-blind manner.
- (b) The visit day in the double-blind treatment period is defined as Week 0 (Day -1). The day after Day -1 is defined as Day 1. All visit windows are in reference to the date of scheduled visit.
- (c) Subjects who prematurely discontinue the study during the placebo lead-in period or double-blind treatment period will be requested to visit the study site for the end-of study examinations within 7 days after the day of study discontinuation, wherever possible, and will be assessed in the same way as at Visit 8 (except for blood sampling for pharmacokinetics).

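### Subjects who stop before Week 4 give no drug concentration, so the exploratory exposure-tolerability analysis is conditional on staying to Week 4; a PK tube at the early termination visit would be a cheap improvement

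*Protocol*

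**What the plan says.** In Protocol section 9.3.4 the only visit with pharmacokinetic sampling is the one at "4 weeks after the start of double-blind treatment period (Day 28 ± 3; Visit 6"). The lists for Weeks 1, 2 and 6 have none. Section 9.3.5 adds Visit 8 but qualifies the item: "Pharmacokinetic sampling (not performed at early termination"). Appendix A note (c) says the same of subjects who stop early, who "will be assessed in the same way as at Visit 8 (except for blood sampling for pharmacokinetics").

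Section 9.1.17.1 ties PK blood to other blood work: "Blood samples will be collected in concurrence with blood collection for clinical laboratory tests". It also asks for the sampling time and the times of the last two doses. Clinical laboratory blood is on the list for the early termination visit.

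Section 13.1.4 will estimate AUC, Cavg and Cmax for each subject, and "their correlation with relevant pharmacodynamic parameters (efficacy and tolerability/safety) will be explored". It then defers the detail: "The population pharmacokinetic analysis plan will be prepared separately". Neither the Protocol nor the SAP says how a subject without a sample is to be handled.

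**The concern.** The missing concentrations are unlikely to be a random subset. Protocol section 4.1.2 reports of earlier studies that "Most TEAEs were mild or moderate and occurred within the first 2 weeks of treatment", which is before the first PK sample. If higher exposure makes an adverse event more likely, and events lead some subjects to stop, those who stop early will tend to have had high exposure. They supply the event but not the concentration. Early withdrawals for suicidal risk under section 7.5.1 are lost in the same way. This matters because section 4.1.3 reports suicidal ideation in 6.6% on 10 mg against 1.6% on placebo in the earlier Japanese study CCT-003.

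At stake is the exposure-tolerability relation in 13.1.4: an analysis of those who stayed would tend to understate it. Section 4.1.1 names CYP2D6 as the primary enzyme, so low activity is one plausible source of high exposure. Pharmacogenomic sampling is optional, so that covariate will be unavailable for some subjects.

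**Working it through.** **1. Where PK blood is taken.** Post-baseline laboratory blood is scheduled at Visit 6 and at Visit 8 or early termination. PK blood is taken at Visits 6 and 8 and excluded at early termination. A subject who stops before Visit 6 therefore has no planned concentration; one who stops after Visit 6 has that sample.

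**2. How many subjects.** 160 per group gives 2 × 160 = 320 on active drug. No dropout rate is stated. If 1% to 10% stop before Week 4 (an assumption), that is 3 to 32 subjects.

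**3. Would a sample at early termination be informative?** Section 4.1.1: "The T1/2 of Lu AA21004 was approximately 66 hours". Five half-lives are 5 × 66 / 24 = 13.75 days, which reproduces the protocol's own figure of about 2 weeks to steady state. The fraction remaining d days after the last dose is 2^(−24d/66):

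| Days after last dose | 1 | 3 | 5 | 7 | 10 | 14 |
|---|---|---|---|---|---|---|
| Fraction remaining | 78% | 47% | 28% | 17% | 8% | 3% |

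On a constant dose, the fraction of steady state reached is 1 − 2^(−24d/66): 83% at Day 7 and 97% at Day 14. The 20 mg group takes 10 mg in Week 1, so its approach to the 20 mg steady state starts a week later.

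The protocol also gives an accumulation index of 5 to 6, which corresponds to 1 − 1/5 = 80% to 1 − 1/6 = 83% remaining per day, against 78% from the half-life. At 7 days that would leave 0.80^7 = 21% to 0.833^7 = 28%, so the table is if anything slightly low for a typical subject.

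**4. Size of the bias: first illustration.** All rates are assumed. Log exposure is standard normal; 30% have a tolerability event at average exposure; the true odds ratio is 2.0 per SD of log exposure; and only subjects with an event stop, with the same dependence on exposure. Subjects without a sample are dropped.

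| Stop before Week 4 | Of 320 | Odds ratio among sampled | Subjects with an event who are still sampled |
|---|---|---|---|
| 3.1% | 10 | 1.88 | 90% |
| 7.0% | 22 | 1.77 | 78% |
| 12.5% | 40 | 1.57 | 61% |

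With a true odds ratio of 1.5, the sampled value is 1.46, 1.39 and 1.30 at 2.4%, 5.7% and 10.9% stopping.

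**5. Second illustration, on another exposure scale.** Assume 320 active subjects, a true odds ratio of 2.0 per doubling of exposure, and 10 to 34 early stops for adverse events.

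- Unsampled subjects dropped: 1.90 to 1.56.
- Unsampled subjects given the typical exposure: 1.83 to 1.45. Model prediction without the subject's own data therefore does not repair the estimate.
- One early termination sample 1 to 7 days after the last dose, with 80% attending: about 1.94 to 1.76.

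**The case against.** The strongest case against is that little rests on this. Population PK is an additional objective and the correlation is only to be explored. SAP sections 3.1.1 and 3.1.2 summarise adverse events, including those leading to discontinuation and those by time of onset from Day 1, by treatment group and without PK data. That stands, and it limits the weight of the point.

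A reader might infer that the analysis sees only subjects who tolerated the drug. The documents do not support that. Section 4.1.2 goes on to say that adverse events were mostly transient and as a rule did not end treatment. Subjects with early events who continue are sampled at Week 4, and those who stop later keep their Visit 6 sample. In the first illustration 61% to 90% of subjects with an event still have one.

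A reader might also infer that early discontinuation cannot be related to exposure at all. It is true that no subject who stops before Week 4 has a measured concentration. But dose is known for everyone, a population model can predict exposure, and genotype may exist for those who consented. Whether any of this is planned is not stated in the Protocol or SAP. A separate plan cannot, however, recover samples that were never drawn.

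The magnitude is also uncertain. With 320 subjects and a 25% event rate, the standard error of the log odds ratio is about 0.18 to 0.26 for an exposure CV of 60% to 40%. A fall from 2.0 to 1.85 is ln(2.0/1.85) = 0.08, under half a standard error. A fall to 1.55 is ln(2.0/1.55) = 0.25, about 1 to 1.4 standard errors.

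Finally, the added sample is imperfect. The early termination visit is timed from discontinuation, and only where possible, so time since the last dose is not capped at 7 days. The 66-hour half-life may also not fit subjects with unusual clearance. These points limit the benefit without cancelling it.

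**Conclusion.** The point holds as an inexpensive improvement to an exploratory analysis. The passages agree with each other, so this is a design choice and not an inconsistency. The documents give no reason for the exclusion.

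The exposure-tolerability analysis is conditional on staying on drug to Week 4 and is probably biased toward no relation. Under the assumed rates a true odds ratio of 2.0 per doubling appears as about 1.9 to 1.5. This rests on assumed event and early-stopping rates and on stopping that depends on exposure. If few subjects stop early, as section 4.1.2 suggests, the bias is at the small end.

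It would be wrong to read this as a threat to the trial's efficacy or safety conclusions: the primary analysis and the adverse event tables are unaffected.

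**What to change.** In Protocol section 9.3.5 and in Appendix A (the PK row and note c), take the PK tube with the laboratory blood already drawn at the early termination visit of any subject dosed in the double-blind period. Collect it in all three groups to keep the blind; section 9.1.17.1 already provides for identifying placebo samples so that they are not assayed. Record the sampling time and the last two dose times as that section requires, and flag these samples as off-treatment in the population PK dataset.

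The cost is one extra tube at a venepuncture already planned, plus assays for early terminators on active drug. Some samples will be pre-steady-state or many days after the last dose, all depend on reported dose times, and subjects who do not attend will still have none.

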9.3.6 Follow-up Period

A safety follow-up assessment will be conducted at 12 weeks after the start of double-blind treatment period (Day 84 ± 5). For subjects who prematurely discontinue the study during the placebo lead-in period or double-blind treatment period, the follow-up assessments will be made 28 ± 5 days after the last dose of the study medication. The follow-up assessments may either be conducted as a visit to the site or as a telephone contact. In the follow-up, the following will be assessed: outcomes of AEs continuing at Visit 8 or early termination visit, new SAEs developing during the follow-up period, and special interest AEs will be assessed. Female subjects of child-bearing potential will be asked to confirm whether they are pregnant or not.

9.3.7 Post Study Care

The study medication will not be available upon completion of the subject's participation in the study.

9.4 Biological Sample Retention and Destruction

Samples of 5-mL whole blood collected for pharmacogenomics will be stored frozen at the pharmacogenomic specimen storage facility (see the contact listed in the attachment 1; hereinafter referred to as specimen storage facility).

The collected samples will be retained for 20 years from the day when a first pharmacogenomic sample was collected during the study.

When subjects request disposal of a stored sample during the retention period, the site will ask the specimen storage facility to destroy the sample via the sponsor according to the procedure. The specimen storage facility will destroy the sample in accordance with the procedure, and notify the site and sponsor. However, any samples should not be destroyed if all the documents

(including medical records) have been destroyed which could identify the subject, and it is impossible to link the sample to the subject.

Even if the sample can be linked to the subject, when pharmacogenomic investigation has been conducted, the remaining sample will be destroyed and the results of pharmacogenomic investigation of the anonymized subject will be retained by the sponsor.

The sponsor will build a management system required for protection of the subject's personal information, define standards for collecting, storage, and destruction of samples, and prepare appropriate procedures.

10.0 PRETREATMENT EVENTS AND ADVERSE EVENTS

10.1 Definitions

10.1.1 PTEs

A PTE is defined as any untoward medical occurrence in a clinical investigation subject who has signed informed consent to participate in a study but prior to administration of any study medication; it does not necessarily have to have a causal relationship with study participation.

10.1.2 AEs

An AE is defined as any untoward medical occurrence in a clinical investigation subject administered a drug; it does not necessarily have to have a causal relationship with this treatment.

An AE can therefore be any unfavorable and unintended sign (e.g., a clinically significant abnormal laboratory finding), symptom, or disease temporally associated with the use of a drug whether or not it is considered related to the drug.

